4.2.3. Sensitivity analyses

The primary analysis described in Section 4.2.2 will be repeated on the PP analysis set, and on the Safety analysis set if any participant receives treatment other than the one to which was randomized.

None of the IEs specified in Section 1.1.1 for the primary estimand are applicable for the PP analysis set, as none of them can occur in participants within the PP analysis set (because of criteria in Table 2). All available HIV-1 RNA data from the monotherapy period on the PP analysis set will be used for the sensitivity analysis.

The maximum VLD calculated for each participant on the PP analysis set will be used for CCI [REDACTED].

4.2.4. Supplementary analyses

[figure not shown]
4.2.4.1. Summaries of HIV-1 RNA Change from Baseline by Visit

Change from baseline in plasma HIV-1 RNA will be calculated for each participant at each assessment time point during the monotherapy and Follow-Up periods in the original and log10 scales. Change from Baseline at each assessment time point during monotherapy and Follow-Up will be summarized in original and log10 scale using descriptive statistics as described in Section 4.1.1.

Mean and 95% CI of change from baseline in plasma HIV-1 RNA in the log10 scale will be plotted by visit for the monotherapy period.

These analyses will be performed on the FAS, PP analysis set, and Safety analysis set if any participant receives treatment other than the one to which they were randomized.

CCI

CCI

4.3. Secondary Endpoint(s) Analyses

4.3.1. Definition of endpoints/estimands

Safety Endpoints

• Incidence of AEs• Severity of AEs• AEs leading to study treatment discontinuation• Change from baseline in liver panel laboratory parameters• Maximum toxicity grade increase from baseline in liver panel laboratory parameters
PK Endpoints
Derived VH4004280 and VH4011499 PK parameters including:

- Maximum observed plasma drug concentration (Cmax)
- Time to maximum observed plasma drug concentration (tmax)
- Concentrations on Day 11 for VH4004280 and VH4011499

For definition of secondary estimands see Section 1.1.1.

4.3.2. Main analytical approach

All secondary Safety and PK analyses will be performed on the Safety and PK analysis set, respectively.

4.3.2.1. Adverse Events analyses

AEs will be coded to the preferred term (PT) level using the Medical Dictionary for Regulatory Affairs (MedDRA) using the latest version at time of database release. AEs will be graded by the investigator according to the Division of AIDS (DAIDS) Criteria Version 2.1.

The number and percentage of participants reporting AEs during the monotherapy period will be summarised using the following categories and subcategories:

- AEs
 - By System Organ Class and Maximum Grade
- AEs leading to permanent discontinuation of study treatment
- Drug-related AEs
 - Overall
 - By Maximum Grade
- Drug-related Non-serious AEs
- Common ($\geq 5\%$) non-Serious AEs
- SAEs by System Organ Class and Maximum Grade
- Drug-related SAEs

The Common ($\geq 5\%$) non-Serious AEs display will also include the number of events of an AE.

Selected displays from the above list will be repeated for AEs with onset during the Follow-Up period and during either the monotherapy or the Follow-Up period. AEs with onset in the monotherapy period which continue in the Follow-Up period will only be included in AE summaries for the monotherapy period. See OPS for the exact AE tables to be repeated for Follow-Up and monotherapy + Follow-Up.

A listing of all AEs and a listing of reasons for considering as SAE will be provided.

All planned AE displays are provided in the OPS document.

4.3.2.2. Liver panel laboratory analyses

Change from baseline values for liver panel laboratory parameters will be summarised by visit. Visits up to Day 11 (inclusive) will exclude any liver panel values assessed under SoC, if SoC starts earlier for any reason, in line with the Estimand definition (Section 1.1.1).

Laboratory toxicities will be graded according to the DAIDS Criteria Version 2.1.

For liver panel lab tests that are gradable by DAIDS (e.g. ALT, AST), summary of worst-case grade increase from baseline grade will be provided. This summary will display the number and percentage of participants with a maximum post-baseline grade increase from their baseline grade (e.g. for participants with maximum increase from Baseline to grade 4 the number and percentage of them will be displayed, same for increase to grade 3, 2 and 1). Also, maximum increase subtotals (i.e. max increase in grade to any grade between 1 and 4, max increase to grade 2-4 or max increase to grade 3-4) will be included. The grade increases are determined by comparing the baseline grade to the worst-case post-baseline grade (e.g., Increase to Grade 1, Increase to Grade 2 etc.) and maximum grade increase subtotals (e.g., Increase to Grades 1 to 4, Increase to Grades 2 to 4, Increase to Grades 3 to 4). The grading subtotals are determined by adding the counts for each worst-case grade change within the subtotal category, e.g., 'Increase to Grades 1 to 4' is a subtotal of all worst-case increases to Grade 1, to Grade 2, to Grade 3, and to Grade 4. Participants with missing baseline value are to be assumed to have a Grade 0 at baseline. The determination of the worst case during the post-baseline period takes into account both planned and unscheduled assessments.

This summary will be produced while participants are under the monotherapy period, as well as overall (i.e. monotherapy and Follow-Up periods).

Liver panel data for participants with at least one abnormal lab value will be included in the listing of chemistry laboratory parameters.

More details of all planned displays are provided in the OPS document.

4.3.2.3. Pharmacokinetic Analyses

Pharmacokinetic parameters for VH4004280 and VH4011499 will be calculated by standard non-compartmental analysis according to current working practices and using the currently supported version of WinNonlin. All calculations of non-compartmental parameters for the End of Study analysis will be based on actual sampling times. For the calculation of the Area under the concentration-time curve (AUC), the linear trapezoidal

method will be employed for all incremental trapezoids arising from increasing concentrations and the logarithmic trapezoidal method will be used for those arising from decreasing concentrations (i.e., Linear Up/Log Down calculation method in Phoenix WinNonlin Professional). A minimum number of three data points (not including Cmax) should be used in calculating λz . The pharmacokinetic parameters described in [Table 3](#) will be determined from the plasma concentration-time data, as data permits and they will be included in the final SDTM datasets.

As per the PK Estimand definition in Section [1.1.1](#), in case of discontinuation of VH4011499, only serum concentration data up to the time of discontinuation of VH4011499 will be used in derivation of VH4011499 PK parameters.

Table 3 Definition of PK parameters

Compound	PK Parameter	Definition
VH4004280 & VH4011499	C_{\max}	Maximum observed plasma concentration
VH4004280 & VH4011499	T_{\max}	Time to C_{\max}
VH4004280 & VH4011499	C_{11}	Concentration on Day 11
VH4004280	$AUC_{0-\infty}$	Area under the plasma concentration vs time curve from time zero hours to infinity
VH4011499	AUC_{0-t}	Area under the plasma concentration time curve from time zero to the last quantifiable time point
VH4004280 & VH4011499	AUC_{0-11}	Area under the plasma concentration time curve from time of first dose to Day 11

Note: Additional Parameters may be included as required

At Interim analyses, preliminary PK data will be analysed by CPMS to select appropriate doses for Part 2 of the study.

Summaries of PK concentration values and PK parameters

All pharmacokinetic analyses will be performed on the Pharmacokinetic Analysis Set. For the End of Study analysis, the following apply:

For each compound, pharmacokinetic concentrations collected within the PK analysis visit window (see Section [6.2.4](#)) will be summarised at every scheduled time point using descriptive statistics. PK concentrations sampled outside the PK sampling windows will

be included in listings and in subject level figures but will not be included in data summaries.

For each compound, derived PK parameters (excluding AUC_{0-11}) will be summarised using descriptive statistics (AUC_{0-11} will be used only for analyses to explore relationship between PK exposure and safety/immunologic endpoints; see Section 4.6.3 and Section 4.6.4).

PK concentrations derived after discontinuation of study treatment will be excluded from PK data summaries, in accordance with the ‘while on-treatment’ strategy for IE, as described in [Table 1](#).

If a participant takes an incorrect dose or miss a dose, PK concentrations and PK parameters inferred until the next dose (in case more than one dose is administered during the monotherapy period) or until the end of monotherapy period (if there is only one dose or if incorrect dose is the last one) may be excluded from PK data summaries, as instructed by CPMS prior to final database lock.

The following figures will be produced:

- A by-participant graph of concentration data over time, on linear and semi-logarithmic scales
- Graph of geometric mean of concentration data over time, on linear and semi-logarithmic scales
- Individual and box plot of PK parameters

Listings of PK concentration and PK parameter values will be produced.

4.3.2.4. Additional Estimands for PK analyses

In case prohibited medications have been used during the monotherapy period, the summary of PK concentrations by visit will be repeated using a “while on-treatment” strategy for the Intercurrent Event of prohibited medication use. This implies that PK concentrations derived after use of prohibited medication will be excluded from PK data summaries.

[figure not shown]
4.3.2.5. PD and PK/PD analyses

The relationship between dose and VLD, and the relationship between PK parameters and VLD will be explored separately by CPMS. These analyses will be described in a separate CPMS report.

CONFIDENTIAL

218307

[figure not shown]
CCI

CONFIDENTIAL

218307

[figure not shown]
CCI

CONFIDENTIAL

218307

CCI

CCI

4.5. Other Safety Analyses

Other safety analyses will be based on the Safety Analysis Set, unless otherwise specified.

4.5.1. Extent of Exposure

If more than one study treatment dose is administered in the monotherapy period (e.g. Part 1b) or if actual dosing data is available (i.e. drug accountability and whether each container includes active drug vs. placebo), summary of exposure will be provided and will include number and proportion of participants received one/two/more doses and/or summary of cumulative actual dose.

A listing of Exposure Data will also be created.

See OPS for further details.

4.6. Other Analyses

4.6.1. Subgroup analyses

No subgroup analyses are planned.

4.6.2. Other Pharmacokinetic Analyses

All other pharmacokinetic analyses will be performed on the Pharmacokinetic analysis set.

For other pharmacokinetic statistical analyses:

- If any PK parameters are derived after discontinuation of study treatment, these will be excluded from statistical analyses in accordance with the “while on-treatment” strategy for IE as described in [Table 1](#).
- If a participant takes an incorrect dose or miss a dose, PK parameters inferred until the next dose (in case more than one dose is administered during the monotherapy period) or until the end of monotherapy period (if there is only one dose or if incorrect dose is the last one) may be excluded from the statistical analyses, as appropriate.

4.6.2.1. Dose Proportionality Assessment

Dose proportionality may be assessed if Part 2 is activated for a compound, following guidance from CPMS prior to final database lock.

Power Model

The analysis will be based on selected available PK parameters. No imputation will be done for missing PK parameters for any participant.

Endpoint / Variables

• For VH4004280: C_{max}, AUC_{0-inf}• For VH4011499:
◦ First dose (Day 1): C_{max}, AUC_{0-t}◦ Second dose (Day 6): C_{max}, AUC_{0-t}
Model Specification

• Dose proportionality of PK parameters will be assessed using the following power model:$y = \alpha * dose^{\beta}$where y denotes the PK parameter being analyzed and dose denotes the dose administered to a subject.• Dose proportionality implies that $\beta = 1$ and it will be assessed by estimating β along with its confidence interval.• β will be estimated by regressing the \log_e transformed PK parameter on the \log_e dose as shown in the following fixed effects model below:

$\log_e y = \log_e \alpha + \beta \log_e dose$
Model Results Presentation

Table: Estimates of slope β will be reported in a Table along with corresponding 90% confidence intervals and number of participants corresponding to the analysis.
 
Figure: Comparative plots will be provided showing individual subject values by dose for each of the PK parameters, together with the predicted PK parameter value from the Power Model.

ANOVA method

If power model does not show dose proportionality, dose proportionality may be assessed by an analysis of variance (ANOVA) model.

PK parameters will be dose-normalised prior to \log_e -transformed by multiplying by reference dose / dose. Dose-normalised PK parameters will be analysed separately using a fixed effects ANOVA model for treatment (dose). Point estimates for the adjusted means on the \log_e scale, the mean difference between each dose (test) and the reference dose and associated 90% confidence interval will be constructed using the residual variance. The point estimate and confidence interval will then be exponentially back-transformed to obtain adjusted (least square) geometric means for each treatment (dose), and point estimates and associated 90% confidence intervals for the ratio test/reference. The reference dose will be chosen based on the lowest clinically relevant dose over which PK can be adequately described, with each other dose as the test doses in the construction of the ratio $\mu(\text{test})/\mu(\text{reference})$.

Plots will be provided showing individual subject dose-normalised PK parameters versus treatment and will also include the geometric mean and 95% CI for each treatment.

4.6.2.2. Estimation of Accumulation Ratios

Accumulation ratios may be estimated for C_{\max} when more than one dose is administered during the monotherapy period, following guidance from CPMS prior to final database lock.

Accumulation ratios are defined as the ratio of PK parameters from the last administration (e.g. Day 6 for VH4011499 in Part 1b) to first administration (Day 1) as follows:

$$R(\text{PK parameter}) = \frac{\text{PK parameter on Day of last administration}}{\text{PK parameter on Day 1}},$$

$$\text{e.g. } R(C_{max}) = \frac{C_{max} \text{ on Day of last administration}}{C_{max} \text{ on Day 1}}.$$

To estimate the accumulation ratios for each treatment, a mixed-effects ANOVA model will be used on the loge-transformed PK parameters, with a random intercept (for each participant) and fixed effects for the day. Day will be treated as a categorical variable in the model. The Kenward & Roger (KR2) degrees of freedom approach will be used [Kenward & Roger, 2009]. The accumulation ratio will be estimated by calculating the ratio of the geometric least squares (GLS) means of PK parameters between last administration (e.g. Day 6 for VH4011499 in Part 1b) and first administration (Day 1) and the corresponding 90% CI. The GLS means of PK parameters on first administration (e.g. Day 1) and last administration (e.g. Day 6), along with the estimated accumulation ratio and its 90% CI will be displayed. No imputation will be done for missing PK parameters.

For each of the statistical models in Section 4.6.2.1 and Section 4.6.2.2 distributional assumptions underlying the model used for analysis will be examined by obtaining a normal probability plot of the residuals and a plot of the residuals versus the fitted values (i.e. checking the normality assumption and constant variance assumption of the model respectively) to gain confidence that the model assumptions are reasonable.

If there are any departures from model assumptions, alternative models or data transformations may be explored.

CCI

CCI

4.7. Interim Analyses

An informal planned interim analysis will be conducted after 9 participants (i.e., 4 participants per active arm and 1 placebo participant) from Part 1a have completed their Day 11 visit. A second informal planned interim analysis will be conducted after 9 participants (i.e., 4 participants per active arm and 1 placebo participant) from Part 1b have completed their Day 11 visit.

The planned interim analyses will evaluate the PK and pharmacodynamics (antiviral activity) of each respective capsid inhibitor and inform whether a third pre-specified optional dosing arm for each capsid inhibitor will be evaluated in Part 2. Depending on Part 1 results, a higher dose, lower dose, or a dose between the two doses evaluated in Part 1 will be evaluated in Part 2. It is also possible that Part 2 will not be conducted for one or both capsid inhibitors if the doses evaluated in Part 1 adequately describe the exposure-response of each capsid inhibitor. The interim results will also inform future clinical development of both compounds.

CCI

Outputs created in the first interim analysis will include only participants from Part 1a who have completed their Day 11 visit. Other participants from Part 1a who have potentially been randomized at the time of data cut for the first interim but have not yet completed the Day 11 visit will not be included in any of the first interim analysis outputs.

Outputs created in the second interim analysis will include only participants from Part 1b who have completed their Day 11 visit. Other participants from Part 1b who have potentially been randomized at the time of data cut for the second interim but have not yet completed the Day 11 visit will not be included in any of the second interim analysis outputs. Participants from part 1a who have completed their Day 11 visit and were not included in the first interim analysis outputs, will be included in the second interim analysis outputs (in other words, the first interim analysis outputs will be updated to include data from all participants in Part 1a at the time of second interim).

Safety outputs provided at an interim analysis will summarise data across all treatment arms within a study part (e.g. at first Interim, Safety outputs will summarise data from CCI [REDACTED] and placebo collectively). In other words, Safety data summaries will be blinded. Any 'by visit' outputs could include data from the Follow-Up period, if available.

The Tables, Figures and Listings that will be provided at each planned interim analysis are described in the OPS.

CCI

CCI

Additional interim analyses may be performed during the course of the study to inform internal decision-making activities and/or support regulatory requests. No changes to the conduct of the study will be implemented as a result of these analyses.

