7.2. Participant discontinuation/withdrawal from the study

- A participant may withdraw from the study at any time at their own request for any reason (or without providing any reason) or may be withdrawn at any time at the discretion of the investigator for safety, behavioral, or compliance reasons.
- Discontinuing from the study for safety reasons should be infrequent. As described in Section 7.1, participants who meet a safety stopping criteria or who discontinue study intervention due to a safety reason, should remain in the study, continue to comply with all other aspects of the protocol (such as starting the first dose of cART standard of care on Day 11) and be followed according to the SoA (Section 1.3) to the EOS as defined in the protocol.
- Participants will not be replaced if the reason for discontinuation from the study is due to a safety concern, with the exception of SARS-CoV-2 scenarios as described in Section 7.2.1. If participants prematurely discontinue the study for non-safety reasons prior to Day 11 (primary endpoint), additional replacement participants may be enrolled at the discretion of the sponsor and investigator. These replacement participants will be assigned to the same treatment sequence and same dose as the corresponding participant who prematurely discontinued from the study.
- Investigators will contact participants who do not return for scheduled visits or follow-up and encourage protocol compliance.
- At the time of discontinuing from the study, if possible, an early discontinuation visit should be conducted, as shown in the SoA (Section 1.3). The SoA lists the data to be collected at the time of study discontinuation and follow-up and for any further evaluations that need to be completed.
- All data and samples collected up to and including the date of withdrawal of/last contact with the participant will be included in the study analyses. If the participant withdraws consent for disclosure of future information, the sponsor may retain and continue to use any data collected before such a withdrawal of consent.
- If a participant withdraws from the study, the participant may request destruction of any samples taken and not tested, and the investigator must document this in the site study records.

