3. ANALYSIS SETS

Analysis Set	Definition	Analyses Evaluated
Screened	
 • All participants who are screened for eligibility 	Study Population

Analysis Set	Definition	Analyses Evaluated
Randomized	
 All participants who are randomly assigned to study treatment (i.e., VH4004280, VH4011499 or placebo) in the study 	Study Population
Safety	
 All randomized participants who take at least 1 incorrect or correct dose of study treatment Participants will be analyzed according to the treatment they actually received 	Study Population, Safety
Full Analysis Set (FAS)	
 All randomized participants who received at least one correct dose of study treatment Data will be reported according to the randomized study intervention 	Efficacy, Study Population
Per-Protocol (PP)	
 All participants in the full analysis set for whom there were no major protocol deviations that impact the primary analyses Data will be reported according to the treatment actually received Specific details of major protocol deviations that would exclude participants from the PP analysis set are provided in Section 3.1 	Efficacy The PP set will not be used for an analysis if it is the same as FAS
Pharmacokinetic (PK)	
 All participants in the Safety analysis set who had at least 1 non-missing PK assessment (Non-quantifiable [NQ] values will be considered as non-missing values) Data will be reported according to the actual study treatment 	PK

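### SAP 4.7 drops dosed participants who leave the study before Day 11 from the interim safety summaries, and gives two different Part 1a populations for the second interim

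*SAP*

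**What the plan says.** SAP 4.7 sets the population for each interim by Day 11 completion. For the first: "Outputs created in the first interim analysis will include only participants from Part 1a who have completed their Day 11 visit". For the second: "Outputs created in the second interim analysis will include only participants from Part 1b who have completed their Day 11 visit". In both cases the SAP adds that participants randomized but not yet at Day 11 appear in none of that interim's outputs. The paragraph on interim safety outputs says they are summarised across all arms within a study part, and so are blinded, and that by-visit displays may include Follow-Up data. It does not say that safety uses a different population.

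For Part 1a at the second interim, the main clause adds "Participants from part 1a who have completed their Day 11 visit and were not included in the first interim analysis outputs". The parenthesis that restates it says "the first interim analysis outputs will be updated to include data from all participants in Part 1a".

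Elsewhere, SAP section 3 defines the Safety set as "All randomized participants who take at least 1 incorrect or correct dose of study treatment", and SAP 4.3.2 states: "All secondary Safety and PK analyses will be performed on the Safety and PK analysis set, respectively". SAP section 1 describes the interim outputs as a selection of the End of Study outputs. Protocol 7.2 says that data and "samples collected up to and including the date of withdrawal of/last contact with the participant will be included in the study analyses".

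**The concern.** Reaching Day 11 is an outcome observed after dosing, and it can depend on tolerability. A filter on that outcome suits an antiviral or PK summary that needs the full monotherapy period. It does not suit a safety summary, because the person removed may be the one whose data bear most on tolerability. Someone still in monotherapy at the data cut will be counted later, so that omission is a temporary maturity cut and is not at issue. Someone who has left the study never meets the condition and stays out of that interim's safety tables.

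The second-interim wording raises a separate, practical problem. Two programmers working from the same sentence could build different Part 1a populations if anyone withdrew early. One reading would bring back a Part 1a withdrawal that the first interim omitted, while an equivalent Part 1b withdrawal stays out under either reading.

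**Working it through.** **Inputs.** The interim trigger is 4 + 4 + 1 = 9 completers (SAP 4.7). Part 1a has 6 + 6 + 2 = 14 participants (SAP 1.2). Both counts agree with the documents. Withdrawals for a safety concern are not replaced, SARS-CoV-2 scenarios aside; non-safety withdrawals before Day 11 may be replaced (SAP 4.1.1, Protocol 7.2). The visible text gives no withdrawal rate.

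**Who is in the interim safety tables, by participant type**

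| Participant at the data cut | SAP 4.7 filter | Safety set (SAP 3) |
|---|---|---|
| Dosed, completed Day 11 | In | In |
| Dosed, stopped treatment, stayed in study to Day 11 | In | In |
| Dosed, still in monotherapy | Out for now | In |
| Dosed, withdrew from study before Day 11 | Out | In |

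Only the last row is the problem.

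**Either interim, one early withdrawal with an adverse event.** Take 9 completers without that event and 1 withdrawal with it.
- Filter as written: 0/9 = 0% (exact 95% CI 0% to 33.6%).
- Completers plus withdrawals: 1/(9 + 1) = 1/10 = 10.0% (exact 95% CI 0.3% to 44.5%).

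**Second interim, Part 1a**

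| Scenario | Main clause (completers) | Parenthesis (all) |
|---|---|---|
| No early withdrawal | 14 | 14 |
| One withdrawal, not replaced | 14 − 1 = 13 | 14 |
| One non-safety withdrawal, replaced | 14 | 14 + 1 = 15 |

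This assumes that every other Part 1a participant has reached Day 11 by then. If the unreplaced withdrawal had an adverse event seen in nobody else, the table shows 0/13 or 1/14 = 7.1%.

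**How often it could arise.** With an assumed individual probability d of leaving before Day 11 for any reason, the chance of at least one among 14 is 1 − (1 − d)^14. For d = 2%, 5% and 10% this is 25%, 51% and 77%. These rates are assumptions and cover all withdrawals, not only those caused by adverse events.

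**The case against.** The strongest reply is that this is a data-maturity rule for an informal look. The sentences that follow the filter concern participants who have not yet reached Day 11, and the authors' own paraphrase speaks of all Part 1a participants, so they probably did not mean to discard withdrawals. An interim cut narrows an analysis set without contradicting it, and the protocol's statement about data up to withdrawal may refer to the final analysis.

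The consequences are also limited. The interims evaluate PK and antiviral activity to decide on Part 2, and no visible rule ties that decision to the safety tables. Those tables are pooled and blinded, so they cannot show tolerability by dose. The medical monitor, safety lead and Safety Review Team review safety continuously, and the pausing rules apply per compound without this filter (Protocol 8.3.7 and 10.1.6). Participants who stop dosing should stay in the study, and Protocol 7.2 says: "Discontinuing from the study for safety reasons should be infrequent". For single-dose VH4004280, treatment discontinuation is not possible at all. Finally, parts of SAP 4.7 are redacted and the OPS, which lists the interim displays, is not available here.

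Most of this stands, and it is why the point is minor. It does not change the text. The rule admits only completers, no output type is visibly exempted, and a withdrawn participant is not merely late. Even if the Safety set and the protocol rule do not strictly bind an interim cut, the SAP gives no reason to narrow the safety population by a post-dose outcome. The mismatch over Part 1a lies within one visible sentence, so the redactions do not resolve it.

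**Conclusion.** The concern holds, at minor severity. On the visible text, interim safety summaries leave out any dosed participant who withdraws from the study before Day 11. The second-interim text also gives two Part 1a populations that differ whenever such a withdrawal occurs. Each withdrawal removes one person from a table of about ten. With no early withdrawal, the two readings agree and nobody dosed is lost once all have reached Day 11. The primary estimand and the final safety analyses are unaffected. The conclusion assumes that neither the redacted text nor the OPS contains an exception, which cannot be checked from the public documents; confidence is medium for that reason.

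**What to change.** In SAP 4.7:

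1. Apply the Day 11-completer restriction to PK and antiviral outputs only.
2. Base interim safety outputs, still pooled and blinded as planned, on dosed participants in the study part who either completed Day 11 or withdrew from the study before it. Those still in monotherapy at the cut may be included or reported as a count.
3. State a single Part 1a population for the second interim, in place of the differing main clause and parenthesis, and reword the opening sentence so that it no longer limits the outputs to Part 1b.
4. If the redacted text or the OPS already does this, bring the visible wording into line with it.

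The cost is SAP wording, one extra population flag and minor programming. Data collection, blinding and the interim trigger do not change.
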